- Evaluations will consist of a detailed review of the consent form, demographic survey, physiological measures (e.g., height, weight, blood pressure, pulse), physical function measures, cognitive tests, and surveys to evaluate knowledge, attitudes, and behaviors around technology use, well-being, sleep, lifestyle activities, physical activities, social networks, depression, health status, independent activities of daily living, and activities of daily living. All measures that can be completed remotely prior to visit, with the research assistant outside of the room, or with the research assistant greater than 6 feet from the patient will be.
- Participants will be asked to wear an Apple Watch paired with an iPhone and an Actigraph for 2 weeks prior to starting the intervention. Participants will be given hands-on education on the use of the these devices at baseline and provided on-call support while wearing them. For those who have an iPhone, we will offer to provide the iPhone or if they prefer, we can download the secure physical activity monitoring research app at no cost. This app does not collect personally identifiable information and can be easily removed from their iPhone.

- The pre-intervention MRI scan will be scheduled at this visit and completed prior to intervention start.

Intervention Visits (in-person)

- After 2 weeks of using the Apple Watch paired with an iPhone and Actigraph to measure baseline activity levels, participants will have their first intervention visit.
- The day prior to each intervention visit, research staff will call the participants to complete the COVID-19 clinical screening questions. If participants screen positive, the visit will be canceled.
- All intervention visits will occur at Hampton House Room 398, the Bayview clinic, or Howard County General clinic. Parking will be vouchered for participants, if applicable.
- Universal masking will be used for participants and research staff. Research staff will use a face shield whenever a distance of 6 feet cannot be maintained. Cleaning protocols will occur as per CDC guidelines and only one research participant will be in the room on a given day (only one per cleaning).
- During the first intervention visit:

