- The day prior to the visit, research staff will call the participants to complete the COVID-19 clinical screening questions. If participants screen positive, the visit will be canceled.
- Participants will have a third cognitive and functional evaluation 9 months post-intervention (12 months post-baseline) to test the potential durability of any benefits observed immediately post-intervention.
- Universal masking will be used for participants and research staff. Research staff will use a face shield whenever a distance of 6 feet cannot be maintained. Cleaning protocols will occur as per CDC guidelines and only one research participant will be in the room on a given day (only one per cleaning).
- This evaluation will include the same physiological measures, cognitive and physical function measures, surveys and 2-week Apple watch to wear paired with an iPhone and Actigraph as completed at baseline and post-intervention. All measures that can be completed remotely prior to visit, with the research assistant outside of the room, or with the research assistant greater than 6 feet from the patient will be. After those two weeks, the participants will be asked to either bring the watch to next clinic appointment or return the watch via mail in a pre-paid package.

MRI protocol:

MRI scans will be performed on a 3T Philips scanner housed in the F.M. Kirby Research Center for Brain Imaging at the Kennedy Krieger Institute. This is a research dedicated MRI facility that contains two 3T Philips scanners. The sequences to be completed for this study are as follows:

Structural Scans:

- MPRAGE sequence (repetition time = 8 ms, echo time = 3.6 ms, FOV = 256 mm, matrix = 256 × 256, slice thickness = 1 mm; 200 slices). Acquisition time 6 min 58 sec.

- Fluid-Attenuated Inversion Recovery (FLAIR): The FLAIR structural scan will be an T2 sequence with a $1 \times 1.19 \times 1.20$ mm³ resolution with 160 slices over an FOV of $256 \times 256 \times 256$ mm with TR/TE = 11000/2800 ms. The total scan time will be 5 min 8 sec.
- High-resolution Hippocampus: A high-resolution structural acquisition with a limited field of view covering the bilateral hippocampus is completed using a T2 sequence with TR/TE = 8020/54 ms, a resolution of 0.4x0.4x2.0 mm over a FOV of 179x179x60 mm. The SENSE acceleration factor = 2. The total scan time is 5 min 36 sec.

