It is important to include a control in this study because the video game being evaluated is designed to be multi-modal through integrated, complex cognitive and physical activity. To better isolate the impact of this multi-modal approach relative to physical exercise alone, it is important to compare any benefits of Bandit play to the benefits of the Successful Aging Program with an integrated placebo exercise component. .

In order to minimize bias in the assessment of outcomes of the two treatment arms, the study greatly benefits from blinding the research team as much as possible. Given the nature of the study, the participants will not be blinded.

d. Justification of why participants will not receive routine care or will have current therapy stopped.

N/A. No adjustments will be made to the standard of care in regard to medication or therapy during the study.

e. Justification for inclusion of a placebo or non-treatment group.

The Successful Aging Program will be used as the active control group for this study. This program is an active health education intervention (approximately 60 minutes long) based on staff attention both through lectures from the Prevention Research Center 10 Keys to Successful Aging materials on a variety of topics related to older adults. A short instructor led program (5-10 minutes) of upper extremity stretching exercises (a “placebo exercise”) will be performed during each class to help foster adherence without directly affecting the study outcomes. In addition to the 60 minute in-person instructor led group, participants will be encouraged to spend two hours a week on take-home activities from the 10-key participant workbook and/or work on their personal health goals. We feel this group is necessary to account for the treatment effect caused by frequent visits and exercise alone.

f. Definition of treatment failure or participant removal criteria.

If the participant no longer wishes to be enrolled in the study, they will be excused with no consequence to their ongoing treatment and physician care. Subjects who become suicidal or develop problems that require aggressive treatment during the course of the study will be withdrawn, and followed at their established clinic, if appropriate care can be provided on an outpatient basis. If outpatient care is not appropriate, the clinical PI ([name]) will be responsible for admitting subjects.

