Grip Strength will be measured with a dynamometer and captures upper limb muscular strength.

Self-reported whole-body physical and mental tiredness will be measured using the Pittsburgh Fatigability Scale.

IADL outcomes: Self-reported measures of physical function performing Independent Activities of Daily Living (IADLs)

ADLs outcomes: Self-reported measure of physical function performing Activities of Daily Living (ADLs).

Objective #2, Primary Outcome

Brain MRI Volumetrics: We will obtain 3-T volumetric data on a research-dedicated Philips 3 Tesla (T) scanners using previously described methods. We will obtain various volumetric measures, including:

hippocampus, amygdala, mediotemporal cortex, orbitofrontal cortex, striatum, total gray matter, and total white matter using standard software packages including Freesurfer, SPM and MRICloud.

Objective #3, Primary Outcome:

Same as primary objective, primary outcome

- c. Secondary outcome variables.

Primary Objective, Secondary Outcomes:

Activity outcomes: The following physical activity will be assessed with an Apple Watch paired with iPhone and an Actigraph:

- Summary metrics include: total counts/day (amount); total minutes of activity/day (duration); total bouts of activity/day (duration); levels of activity intensity (sedentary to vigorous) and accumulated time within each activity level.
- We will additionally include a novel, validated metrics, including active (non-rest) time and variability, intensity of movement and daily time- stamped, or diurnal, patterns of low, moderate, and vigorous activities.
- The following data on heart rate will be assessed using the heart rate sensor on the Apple Watch: - Summary metrics include: BPM –beats per minute; resting HR (non-intervention); on-intervention HR; HR variability (Standard deviation of all HR intervals, Standard deviation of the averages of HR intervals in activity bouts.

Neuropsychiatric Symptoms: The following data will be collected to assess for neuropsychiatric symptoms:

- The Patient Health Questionnaire-9 (PHQ-9) depression scale will be used for depression screening measures.
- The Neuropsychiatric Inventory–Questionnaire (NPI-Q) will be used to provide a brief assessment of neuropsychiatric symptomatology.

Lifestyle and Physical Activity: The following questionnaires will be given to assess lifestyle and physical activity.

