the number of patients with TBI seen at the clinical sites and given what is feasible for us to complete the study visits in the time provided through Department of Defense (DoD) grant funding.

Data Analytic Plan:

- Definition and selection of dataset: Using an Intention-to-treat (ITT) design, all randomized participants will be included and followed up as available. The per-protocol (PP) population will include all participants in the ITT population who are compliant with study treatment as defined by >70% session exposure. Baseline demographic and clinical characteristics, including time since TBI, severity, medical comorbidity, and post-concussive symptoms will be included as covariates in the ITT dataset. Pre-post intervention benefits will be assessed using both ITT and PP datasets.
- Basic exploratory analyses will first be conducted, including checking of distributional assumptions, assessment of relationships among covariates, and missing-value multiple imputations.
- Continuous variables will be described by using mean, standard deviation, median, minimum and maximum, and 95% confidence interval for parameter estimation. Graphical display (spaghetti plots) of the outcome scores will also be generated for the 4 visits (baseline, 3 months, 9 months and 12 months) by group. Category and count variables will be described using frequency or proportions.
- Analyses will be conducted using STATA 11.2 (StataCorp, Texas, 2009) or R 2.13.2(2011). All statistical tests will be judged for significance based upon a two-sided p-value of less than 0.05.

e. Early stopping rules.

- If it is deemed that the participant requires a higher level of care (inpatient hospitalization), they will be removed from the study.

8. Risks

a. Medical risks, listing all procedures, their major and minor risks and expected frequency.

We do not expect any anticipated adverse outcomes for the study participants. The risk is minimal and therefore no harm is expected to be done to participants.

Risk associated with study involvement: As this study includes research as part of standard clinical care, there is a minor risk of unintentional release of protected health information. Risks in regard to assessments are limited to boredom, fatigue, and frustration. Additionally, given the time spent outside of their homes, participants risk exposure to COVID-19.

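### The removal rules in 4.f and 7.e are not confined to the 12-week intervention and, read plainly, end outcome collection for participants who deteriorate, including the 12-month evaluation

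*Combined protocol and SAP*

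**What the plan says.** Two sections set rules under which the study team takes a participant out.

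- Section 7.e (Early stopping rules): "If it is deemed that the participant requires a higher level of care (inpatient hospitalization), they will be removed from the study".
- Section 4.f (treatment failure and removal criteria): "Subjects who become suicidal or develop problems that require aggressive treatment during the course of the study will be withdrawn". Such participants are then to be "followed at their established clinic, if appropriate care can be provided on an outpatient basis"; otherwise the clinical lead is responsible for admission.

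The intervention lasts 12 weeks, and enrollment lasts 12 months (4.b). On the last visit, section 4.a says: "Participants will have a third cognitive and functional evaluation 9 months post-intervention (12 months post-baseline".

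Section 7.b lists self-reported IADL and ADL among the primary outcomes of Objective 1. For Objective 3 (durability), the primary outcome entry is "Same as primary objective, primary outcome". Mood and health status (PHQ-9, Geriatric Depression Scale, EQ-5D, SF-36) are secondary outcomes in 7.c.

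Section 7.d says that the intention-to-treat analysis includes everyone randomized, with follow-up to the extent it can be had, and it names multiple imputation.

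**The concern.** A safety rule needs to stop the study intervention. It does not need to stop measurement. Sections 4.f and 7.e do not separate the two: they take the person out of the study, at any time in the 12 months, and the only follow-up mentioned is clinical care.

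This matters for two reasons. First, the missing values would not be a random subset. Removal follows suicidality, aggressive treatment or hospitalization, and people in that state plausibly have worse IADL, ADL, mood and health-status scores than those who stay. The analysis set would formally include them but would hold no later data on them. Secondly, once the 3-month assessments are done, removal protects nobody from a study treatment. Its main effect is the loss of the Objective 3 evaluation.

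No link between these triggers and the cognitive tests or MRI measures is shown.

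**Working it through.** **Reading the text.** The plan gives no figure on this point to reproduce, so the first step is to set the relevant sections side by side.

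- *Time limit.* Section 4.f applies throughout the study, and 7.e gives no window. The intervention ends at month 3 and enrollment at month 12, so both rules remain in force for 9 months without study treatment.
- *Follow-up after removal.* The clinic follow-up in 4.f depends on outpatient care being appropriate, and the next sentence deals with admission. It describes care, not outcome collection.
- *Sections that allow partial participation.* Section 4.b lets participants choose how many follow-up visits to attend, 4.g lets them leave any component or the whole study, and 8.b lets them drop one part and continue data collection in others. All three concern the participant's own choice. They also show that the protocol can separate a part of the study from the whole, which 4.f and 7.e do not do.
- *Intention-to-treat statement (7.d).* It neither says that removed participants are still assessed nor rules it out.

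**Which objectives are reached.** Removal before the 3-month visit can affect Objectives 1, 2 and 3. Removal after the 3-month visit and scan can affect only Objective 3.

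**Size.** The plan gives a total of 66 (7.d). Everything else is assumed: 1:1 allocation (33 per arm), outcome SD = 1, *k* excess removals in one arm, and a deficit of *w* SD that imputation does not recover.

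- Standard error of the arm difference = √(2/33) = 0.246 SD.
- Bias = (*k*/33) × *w*.
- Two-sided error rate = P(|Z + bias/SE| > 1.96), nominally 5%.

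| *k* | *w* (SD) | Bias (SD) | Bias / SE | Error rate |
|---|---|---|---|---|
| 0 | any | 0 | 0 | 5% |
| 1 | 0.5 | 0.015 | 6% | 5.04% |
| 2 | 0.25 | 0.015 | 6% | 5.04% |
| 2 | 0.5 | 0.030 | 12% | 5.17% |
| 2 | 1.0 | 0.061 | 25% | 5.70% |
| 4 | 1.5 | 0.182 | 74% | 11.4% |

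The last row is a ceiling and is unlikely.

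**How often such a gap arises by chance.** Let removals in the two arms be independent Binomial(33, *p*) with the same true rate *p*:

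| *p* | Expected removals (66*p*) | P(gap ≥ 2) | P(gap ≥ 4) |
|---|---|---|---|
| 1% | 0.7 | 0.06 | 0.0005 |
| 2% | 1.3 | 0.16 | 0.005 |
| 5% | 3.3 | 0.38 | 0.05 |
| 10% | 6.6 | 0.53 | 0.15 |

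These gaps are random. With equal deficits in the two arms their expected bias is zero. A systematic bias needs removal rates or deficits that truly differ between arms.

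**The case against.** The strongest reply is that the harm is inferred. No sentence says that assessments stop. The one sentence on follow-up of randomized participants, in 7.d, makes no exception for those the team removes. Both rules are short answers to form prompts about safety, so one could hold that they govern participation while 7.d governs the data. This stands as far as it goes: the text is not conclusive. But staff applying 7.e as worded would have no instruction to assess a removed participant, and 7.d does not supply one.

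The plan does name multiple imputation, and 7.d lists severity, medical comorbidity and post-concussive symptoms as covariates. For a removal after month 3, the 3-month values would help to impute the 12-month value. This reduces the problem. It does not remove it, because the plan does not say how imputation handles values missing because of later deterioration.

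The argument that no treatment is left to stop applies only after the 12 weeks. During them the rule does stop sessions, and the complaint is only that it stops assessments as well.

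The numbers are small and every driver is assumed. Untreated major mental illness is an exclusion (section 5), which should make these events less common. Missed visits by choice (4.b) may be a larger source of missing data. A difference between arms is conceivable during the intervention, because the game arm has 24 to 36 visits and the control arm 12, so staff have more occasions to notice a trigger. That is plausible, not shown.

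Finally, keeping the survey outcomes is not always easy. Section 4.a lists among the surveys "depression, health status, independent activities of daily living, and activities of daily living", and its instruction on "All measures that can be completed remotely prior to visit" favors remote completion, but it does not name IADL and ADL as remote measures. Someone in hospital may be unable to answer.

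**Conclusion.** The concern holds as a minor design point, with medium confidence. Sections 4.f and 7.e have no time limit and provide for no later study assessment. Followed as written, they would lose outcomes because of clinical deterioration, and after month 3 they would do so without stopping any study treatment. That they end outcome collection is the plain reading, not an explicit statement.

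The likely effect on the arm difference is small: a few hundredths of an SD at most in the moderate case, and none if removals and deficits balance. This rests on the assumptions of 33 per arm, the chosen excess removals and the chosen deficits; the plan gives no removal rate to replace them. The exposed outcomes are IADL and ADL and the secondary mood and health-status scales.

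**What to change.** Reword 4.f and 7.e so that suicidality, aggressive treatment or hospitalization ends the study intervention only, with clinical decisions unchanged. Add that the 3- and 12-month assessments continue where consent and condition permit: surveys, including IADL and ADL, remotely, and in-person tests at the usual clinics where possible. Report removals by arm and by timing (before or after the 3-month visit). A delta-adjusted sensitivity analysis for IADL and ADL is optional.

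The cost is wording in two sections and a few extra contacts, with no new staff or procedures. Some people who are suicidal or in hospital will be unable or unwilling to take part, and in-person measures (SPPB, grip strength, MRI) may still be missing for them.

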[name], co-I of this study, has successfully demonstrated the feasibility of implementing Bandit 1 hour/day, 3 days/week among older adults (n=16; mean age= 79) in an independent-living retirement community who exhibit varying levels of physical function and disability, including Parkinson's disease, COPD, and lower-limb amputation. Participants were 100% compliant and, as shown in the Figure below, most showed steady improvements in performance over game sessions, with the exception of one participant who discontinued due to vertigo from Meniere's disease. Anecdotal quotes from participants during and after game play include: "Bandit, you stinker, you're supposed to eat the shark on this level, not the fish!" and "This is 'sneaky exercise' because you're not actually thinking about how much you're moving..." We have recently completed focus groups with 100% compliance that confirm high levels of motivation to play Bandit. This pilot study motivates our proposal to extend this intervention to aging adults with past TBI to innovate intervention designs that use safe, video game technology to promote complex, integrated cognitive-motor behavior important to daily independent functions (e.g., shopping, driving, cooking).

[figure not shown]
4. Study Procedures

- a. Study design, including the sequence and timing of study procedures (distinguish research procedures from those that are part of routine care).

Study Design: Randomized Controlled Trial

Study Population: Patients 40 years of age or older with a remote history of TBI (>2 years) and evidence of mild cognitive impairment

Sequence and Timing of Study Procedures: See Study Design Figures below. All procedures listed after consent are research procedures. Enrollment will occur at the ABI and MATC clinics.

Patient Identification (in-person or remote)

- Potential participants are established patients of clinical PI, [name] and clinical co-Investigators.

- The research team will identify individuals that meet the inclusion criteria and no exclusion criteria for the study.

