An interim-analysis will be performed on the primary outcomes when 1/3rd (n=22) of patients have been randomized and have completed the 12 weeks of study intervention and post-intervention follow-up visit. The interim-analysis will be completed by a statistician blinded from the treatment arm. The statistician will report to the independent data safety monitoring board (DSMB). The DSMB will have unblinded access to all data and will discuss the results of the interim-analysis. The DSMB will decide on continuation of the trial. If the DSMB feels a case of futility is present, they will discuss with the investigators, and IRB if necessary, to decide on continuation of the trial.

b. Primary outcome variable.

Primary Objective, Primary Outcomes:

Objective #1, Primary Outcomes

Cognitive outcomes: We will assess executive function, psychomotor and perceptual speed, and verbal learning and memory. Four tests will be administered: the Trail Making Test (TMT), the Stroop Test, the Pattern Comparison Test, and the Rey Auditory Verbal Learning Test (RAVLT). The TMT is comprised of two timed parts, A and B, that requires participants to connect numbers in an ascending sequence (Part A measures psychomotor speed) and in ascending alphanumeric sequence, numbers and letters (Part B measure executive function). The Stroop test requires one to name as quickly and accurately as possible the color of ink that color-words are presented in (e.g., “red” presented in blue ink) and assesses one’s ability to inhibit a well-practiced response (word reading) in favor of a less-practiced response (inhibitory executive function). Perceptual speed will be assessed using the Pattern Comparison Test, requiring one to compare as many pairs of 32 line drawings as possible in 30 seconds and to determine whether members of each pair are similar or different. Verbal learning and memory will be assessed with the RAVLT which is comprised of 3 presentations and 3 recalls of a 15-word list as well as a 20-minute delayed recall of the word list.

Physical Mobility outcomes: Performance-based measures of mobility will be performed using the Short Physical Performance Battery (SPPB). Measures include:

- Walking speed, both usual and rapid pace, over a 4 meter course.
- Ability to rise from low chair without using arms.
- Balance: Functional reach and static stands: side-by-side, semi-tandem and tandem.

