Risk associated with magnetic resonance imaging (MRI): MRI can damage or heat implanted or worn metallic objects or jewelry. It can also interfere with the proper functioning of implanted devices (e.g., pacemakers). In the setting of TBI, increased intracranial pressure (e.g., from a subdural hematoma) would be a contraindication for lying flat in the MRI machine for an extended period of time. Lastly, the MRIs will be reviewed for incidental findings, which can be psychologically troubling or lead to need for further work-up, which can be financially, emotionally, and logistically difficult for patients.

Vulnerable Subjects: In some instances, older adults are considered a vulnerable population. There are some risks associated with driving to appointments and exposure to hospital environment.

b. Steps taken to minimize the risks.

Mitigation of risk associated with study involvement: All study personnel are trained in general principles of informed consent, confidentiality, and privacy requirements. A study team investigator will be available by cell phone to speak to staff, subjects, or prospective subjects regarding preventing harm and minimizing risk. Participants may choose to discontinue participation in any portion of the study and continue participation in other components of data collection. If the patient ever has concerns or discomfort arises, the patient may contact the study physician at any time. We have made all elements of the protocol that can be completed remotely so. We will give participants the opportunity to complete 24 longer intervention visits rather than 36 shorter to minimize exposure during travel.

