e. Financial risks to the participants.

Although there are no direct financial risks, if there are abnormal MRI or other study findings, this may lead to further medical workup and financial cost.

9. Benefits

a. Description of the probable benefits for the participant and for society.

Benefits to the participant: There may or may not be benefits to subjects who participate in this study. The participant will receive a thorough neuropsychiatric evaluation and brain MRI at no charge. Participants will also have access to the study physician should they have study or non-study-related health concerns. Should the gaming intervention improve cognitive health as we hypothesize, the patient will have reaped these benefits during the study. If the control arm has interest in trying the intervention, they will also be given that opportunity after the study has convened. Based on the minimal risks of the study and potential benefits, this study has a favorable risk-benefit ratio for participants.

Benefits to society: Benefits to society will include important information that will add to the current body of knowledge on associations between TBI and ADRD. Our study will also contribute to the body of knowledge on complex motor activities as neurocognitive enhancers, for which there are very few studies despite its promise as an intervention strategy. We also hope to introduce a novel, low-risk intervention using complex motor activities in the treatment of TBI. We also customized this intervention to be appropriate for the aging population, a population which is excluded from involvement in current neurocognitive rehab treatments due to physical limitations.

10. Payment and Remuneration

a. Detail compensation for participants including possible total compensation, proposed bonus, and any proposed reductions or penalties for not completing the protocol.

Participants will receive \$70 at each evaluation (Baseline, Follow-Up, and 9-month Follow-Up). Parking is vouchered for participants. Where budget allows, the study team will make efforts to reimburse participants for travel expenses deemed to be a barrier for participation, such as use of rideshare apps.

11. Costs

- a. Detail costs of study procedure(s) or drug (s) or substance(s) to participants and identify who will pay for them.

There are no monetary costs to participants who take part in this study. All study materials, procedures, and human resources will be directly paid for by the study grant.

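### Section 8a names no risk of playing the game, and the protocol describes no adverse-event collection that is comparable between the arms

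*Combined protocol and SAP*

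**What the plan says.** The heading of section 8a asks for a text "listing all procedures, their major and minor risks and expected frequency". The answer opens with "We do not expect any anticipated adverse outcomes for the study participants. The risk is minimal and therefore no harm is expected to be done". It then covers unintentional release of health information, assessments ("Risks in regard to assessments are limited to boredom, fatigue, and frustration"), infection ("given the time spent outside of their homes, participants risk exposure to COVID-19"), MRI, and travel ("There are some risks associated with driving to appointments and exposure to hospital environment"). It gives no expected frequency for any of them.

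Section 6a says that the game is played standing and engages the whole body. Sections 4a and 4b give 24 to 36 game sessions of 60 or 90 minutes, warm-up and warm-down included, against 12 weekly sessions for controls. Section 3 reports the pilot (n=16, mean age 79), in which most players improved "with the exception of one participant who discontinued due to vertigo from Meniere's disease".

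Sections 7b to 7d contain no adverse-event outcome and no event table. Section 7a says: "An interim-analysis will be performed on the primary outcomes when 1/3rd (n=22) of patients have been randomized". Section 7e, on early stopping, contains only a rule for removing an individual. Under sections 8b to 8d, participants may contact the study physician, events that come to light go to the principal investigator, and unanticipated problems and deviations go to the IRB. Section 9a says: "We also hope to introduce a novel, low-risk intervention using complex motor activities in the treatment of TBI".

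**The concern.** The experimental procedure is the one procedure for which 8a names no risk of its own. The investigators' own pilot shows at least one way in which play can end early. A risk section that leaves this out gives staff no prompt about what to look for.

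The larger statistical issue is ascertainment. If events are recorded only when someone volunteers them, the count depends on how often participants meet someone to tell. That opportunity differs between arms by design. A higher count in the game arm could then reflect more contact rather than more harm, and a low count in the control arm could reflect silence. Neither the board at the interim look nor a reader of the final report could separate the two.

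**Working it through.** The plan states no adverse-event rate, safety sample size or safety precision, so there is no figure of its own to reproduce. Four checks follow.

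**1. Is game play among the listed risks?** Set against its heading, 8a addresses privacy, assessments, COVID-19 exposure, MRI, and travel and hospital exposure. The COVID-19 and travel risks do reach the session visits, but they come from getting there and being there. Nothing listed comes from playing: no dizziness, fall or strain.

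**2. What does the pilot show?** The input is 1 discontinuation for vertigo among 16 (section 3).
- Proportion: 1/16 = 6.25%.
- Exact (Clopper-Pearson) 95% interval: 0.16% to 30.2%.

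One event fixes no useful rate. The same sentence of section 3 also reports 100% compliance, which needs reconciling with a discontinuation.

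**3. How unequal is the opportunity to report?** The inputs are the session counts in section 4b.
- Lower end: 24/12 = 2.
- Upper end: 36/12 = 3.

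Game participants therefore have 2 to 3 times the staff contacts over the same 12 weeks. Calls on the day before each visit scale in the same way. Control sessions are also group classes (sections 4a and 4e).

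**4. What could solicited data show?** Assume 1:1 allocation, so 66/2 = 33 per arm (the ratio is not stated), and let p be the true rate in the game arm. The chance of at least one event is 1 − (1 − p)^33:

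| p | Chance of at least one event in 33 |
|---|---|
| 1% | 28% |
| 2% | 49% |
| 5% | 82% |
| 6.25% (pilot proportion) | 88% |

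If no event is seen:
- One-sided 95% upper limit for 33: 1 − 0.05^(1/33) = 8.7%.
- Two-sided 95% upper limit for 33: 1 − 0.025^(1/33) = 10.6%.
- At the interim look, assuming 22/2 = 11 in the game arm, one-sided: 1 − 0.05^(1/11) = 23.8%.

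For a between-arm difference with none in the control arm, Fisher's exact test gives p = 0.053 for 5 against 0 and p = 0.024 for 6 against 0. Six events would be needed.

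**The case against.** Much can be said for the plan.

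- **The pilot event.** The protocol attributes the vertigo to an illness of that participant. A reader might infer that the pilot contradicts 8a or that the game caused the vertigo. Neither is supported. The event sits badly with a statement that no harm is expected, and no more than that.
- **Transfer of the rate.** The pilot sample had a mean age of 79 and included people with Parkinson's disease and limb amputation, both named as exclusions here. The trial enrols from age 40. The pilot proportion is therefore not a forecast, and 88% is only one row of a wide range.
- **Eligibility.** Vestibular disease is not named in section 5. However, the exclusions for conditions that interfere with study procedures, and for inability to sit or stand for an hour of arm exercise, could cover disabling vertigo. The latter wording, and the inclusion of warm-up and warm-down, also mean that a full 60 or 90 minutes of standing play should not be assumed.
- **Existing safety information.** It would be wrong to say that the trial has no safety data. Events and problems are reported to the principal investigator and the IRB, and section 4f withdraws participants who develop serious problems. Balance, fatigability, PHQ-9, NPI-Q, EQ-5D and SF-36 are measured in both arms.
- **The board.** Section 7a lets it see all data unblinded, so one cannot assert that it would be kept from information on harm.
- **The low-risk wording.** It is a hope stated under benefits to society, not a planned conclusion.

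All of this stands, and it narrows the point without removing it. Access to all data does not supply answers to questions that nobody was told to ask. The health scales are taken at evaluations and do not record events. Under section 4b participants choose how many follow-up visits to attend, so someone who stopped because of an event may be missing from them. Nothing requires withdrawals to be tabulated by arm.

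**Conclusion.** The point holds in a limited form. Section 8a omits the risks of playing the game, and the protocol describes no systematically solicited, arm-comparable adverse-event data. With 2 to 3 times the staff contact in the game arm, a comparison of volunteered events would be biased by opportunity to report. The size of that bias cannot be calculated from the documents.

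The evidence does not show that the game is unsafe. Nor would better collection let 33 per arm show that it is safe, since zero events would leave rates up to about 9% open. What solicited data would add is an interpretable count with an honest interval.

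The figures assume 1:1 allocation. Consent pages and any charter for the monitoring board are not in the documents, so the gap is asserted for this protocol text only. This is a worthwhile, inexpensive improvement rather than a flaw that undermines the efficacy comparison.

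**What to change.** 1. **Section 8a.** Reconcile it with section 3: list the risks of game play, and report the pilot discontinuation as 1 of 16 with its stated attribution. Clarify the 100% compliance figure in the same pass.
2. **Collection.** Put one fixed question set (falls, dizziness or vertigo, pain or injury, new medical care) to both arms once a week, on the screening call already made the day before a session. Ask it once a week even where there are two or three calls. Repeat it at the three evaluations through staff who are not the blinded assessors, because the answers could reveal the arm.
3. **Reporting.** Give the monitoring board at the n=22 look, and the final report, a table of events and discontinuations by arm with exact intervals. Base the comparison on the solicited answers, and list events seen or volunteered at sessions separately.

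**Cost.** At about one minute a week, 66 × 12 = 792 minutes, or roughly 13 hours of call time over the trial, plus a short data form and the questions at evaluations. No new visits are needed. The risk statement becomes slightly less favourable. Whether the consent form must change cannot be judged from these documents. Participants know their arm, so equal questioning removes the difference in opportunity to report but not every difference in willingness to report.
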